6.3.4 Recruitment, Enrollment and Retention6.3.5 On Study VisitsMEDICATION MANAGEMENT

Initial visit: The PI will meet with each participant at baseline (Week 0) prior to randomization to prescribe NRT (patch, gum, and/or lozenge) if desired, following a VA prescribing algorithm consistent with current prescribing guidelines.12,79 The session will be either in-person or through the telemedicine (V-tel) clinical services at the SFVAMC CBOCs. NRT will follow standard VA prescribing guidelines and will be based on (1) safety, (2) nicotine dependence level, and (3) participant preference. All participants will be instructed to set a goal of stopping cigarette, e-cigarette, and smokeless tobacco use during the course of study.

NRT monitoring: Following the initial visit, a study psychiatrist who is blinded to group assignment will contact participants in both conditions once monthly by phone to monitor for NRT side effects, adjust dosing, and renew refills. Participants who decline NRT will also receive a brief monthly check-in call to eliminate any potential therapeutic effect of these calls on study outcomes. All participants will remain on NRT as long as is clinically indicated throughout the 24-week study period, as determined by the study psychiatrist. Participants may contact the psychiatrist with any side effects or concerns related to NRT.

STUDY INTERVENTION PERIOD

Intervention condition: Details on the weekly telephone counseling sessions are provided in Section 6.1.4. Study therapists will conduct the sessions from private offices at SFVAMC, and veterans will participate via phone from their home or other location that is convenient for the.

Control condition: Details on the QL control condition are also provided in Section 6.1.4. QL sessions are also conducted via phone, and veterans will participate, as frequently as desired, from their home or other location that is convenient for the.

6.3.6 End of Study and Follow Up

Follow-Up: Follow-up Assessments will occur at Weeks 8, 12, and 24. They will be conducted by phone (reminder call day before) and last up to 2 hours each. Details on the measures administered at these Follow-up Assessments are provided in Section 6.2. Participants who withdraw from the study may receive care through the SFVAMC Smoking Cessation Clinic and/or the Quitline as desired.

6.3.7 Removal of Subjects

Rules for Withdrawing Study Participants from the Study Interventions: Participants will be withdrawn from the study if, in the opinion of the DSMB or the PI, there is: sustained clinically significant worsening of symptoms, unacceptable adverse events judged to be related to study interventions, or any other clinically significant medical (e.g., pregnancy), psychiatric, or substance-use related poor outcome that makes continued study participation unsafe in the clinical judgment of the PI or DSMB members.

6.4.1 Statistical Design

Data analytic plan: Prior to analysis all data will be examined for anomalous and missing values and described in detail. The description of the data is a key aspect of this work as it

informs future studies. Qualitative data (Focus groups and Aim 1) will undergo thematic analysis using a hybrid qualitative methodology incorporating deductive and inductive approaches. For the preliminary codebook for interviews, we will start with deductive codes (based on the interview guide and prior literature). Iteratively, we will add inductive codes (using grounded theory methodologies⁸⁹⁻⁹¹). We will apply codes (phrases that explicitly describe segments of data) to relevant quotations for data sorting. Once a preliminary codebook has been created, a minimum of two coders will assist with coding and will apply initial codes as well as develop new codes following review of each additional transcript. All coders will document the process of creating new codes and any changes in previously determined codes. We will hold weekly meetings with coders to aid in calibration of coding and review and discuss discrepancies if necessary. We will calculate inter-rater reliability (Cohen's k for codes) and will resolve discrepancies to ensure consistent code application across raters and over time (.80 or above will be considered acceptable). We will identify themes (recurring and unifying concepts) during iterative thematic analyses until saturation is reached. 90,92 ATLAS.ti software will be used to organize the unstructured interviews objectively. Quantitative Data: To evaluate feasibility (Aim 1) we will calculate the: a) proportion of those eligible among those screened; b) proportion enrolled among those eligible (goal ≥ 50%); c) the rate of enrollment (goal four participants per month); e) adherence to NRT in those prescribed NRT, defined as total days taking NRT divided by total days prescribed NRT (goal ≥ 70% adherence in intervention condition); e) study completion rate in both conditions. We will also examine iCO and SQC app usage patterns (number of days each app is used per participant self-report and total data used by each app over the study period) in intervention condition participants and examine the relationship between app usage and study outcomes. To assess acceptability (Aim 1) we will calculate the percentage of participants in the intervention condition who rate each of the technology components as moderately acceptable or higher as measured by the SUS^{72,73} and the selfreport questionnaire assessing acceptability of the telephone manual (objective: ≥ 75% participants rate SUS ≥ 70 for iCO and SQC and rate telephone sessions as "moderate" or higher acceptability). Qualitative data will be combined with the quantitative acceptability data in a mixed methods analysis for cross-validation of the techniques. Failure to meet the feasibility and acceptability objectives will drive a major revision of the study protocol for future studies. We will also compare retention rates of the two treatment conditions (proportion of participants in each condition that engages in four or more sessions) (Aim 2 Hypothesis) and in seven- and 30-day point-prevalence smoking abstinence rates. FTND scores, and PCL scores (Exploratory Hypotheses) at Weeks 8, 12, and 24. The randomization procedure should result in covariate effects being distributed equally between the treatment conditions. If, however, the preliminary analyses indicate the treatment conditions vary on potentially confounding variables such as age or number of previous quit attempts, these covariates will be included in a multivariate model. Comparing treatment conditions that include time as a factor, the prototypical model will be a nonlinear mixedeffects model for dichotomous outcomes. Given the limited number of assessment points, the most parsimonious model will be a general linear model for each outcome. Planned contrasts among the intervention condition will directly test each hypothesis. Quantitative

analyses will be performed with SPSS. Results will be reported using CONSORT guidelines and the World Health Organization (WHO) mHealth Technical Evidence Review checklist on mobile Health evidence reporting and assessment (mERA).⁹³

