6.1.3 Selection of Instruments/Outcome Measures

Aim 1: Feasibility and Acceptability of the Intervention

- · Feasibility: We will calculate the: a) proportion of those eligible among those screened in rural and urban areas; b) proportion enrolled among those eligible; c) the rate of enrollment; d) adherence to medications (percentage of days participant takes NRT of total days prescribed); e) total number of sessions completed in each condition; f) iCO and SQC app usage data (intervention participants only); and g) study completion rate. To assess NRT adherence and estimate app usage data, participants will be asked to record daily medication adherence in a paper log using the TLFB method with specific anchor dates in a calendar, which will be mailed to the study team at each assessment time point. Pharmacy refill data will be reviewed at each time point to confirm TLFB self-report of medication adherence.
- · Qualitative Interview (Acceptability): We will conduct a 20-minute semi-structured, audiorecorded telephone interview at Week 8 with intervention condition participants only to

collect in-depth feedback about user satisfaction with features of the overall intervention and its components (telephone sessions, SQC app, iCO monitor). We will use a framework of open-ended questions based on an interview guide developed by the study team, similar to that used in the focus groups with the CAP (see 3B.4), but with a greater emphasis on the acceptability of the intervention and its individual components (telephone sessions, SQC app, iCO monitor) in a therapeutic context during a quit attempt. We will inquire about individual features of each component of the intervention and perceived helpfulness; feasibility and acceptability in rural and urban settings; acceptability of the intervention in a military/ veteran cultural context; anticipated barriers and facilitators of implementation; the balance of adequate therapeutic intervention versus time burden; scheduling; cost-effectiveness; and issues of mobile device accessibility and connectivity. Audio-recordings of the interviews will be transcribed and relevant portions about acceptability of the intervention will be noted.

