cigarette or non-cigarette tobacco on any of the seven and 30 consecutive days prior to the assessment, respectively; and (2) salivary cotinine levels < 10 nanograms/milliliter.⁸⁶ For participants using NRT and for those who reported use of smokeless tobacco, e-cigarettes during the study, abstinence status will be independently verified by a friend or family member. Participants with missing salivary cotinine or those unable to obtain verification from a friend or family member will be considered non-abstinent. Participants will be provided with postage-paid mailers, a collection kit, and detailed instructions for saliva collection and will be asked to collect specimens, store them in their home freezer, and mail them to our lab, where they will be batch shipped on dry ice to the Salimetrics lab for analysis.

- · Nicotine dependence: We will administer the FTND at Weeks 0, 8, 12, and 24.
- PTSD symptoms: We will administer the PCL-5 at Weeks 0, 8, 12, and 24.

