6.1.4 Intervention Administration

Intervention Condition: Participants will receive (1) eight 20- to 30-minute telephone sessions [initial session is aproximately 45-60 minutes]; and use (2) technology components (SQC app and iCO Smokerlyzer) between sessions. The therapist will proactively contact participants for each telephone session and use the accompanying workbook. At Week 0, participants will download the SQC app to their personal smartphones and be instructed to use SQC as much as desired between sessions. Participants will receive a brief training and orientation about features of SQC and will populate SQC with personalized information (planned guit date, triggers to smoke and coping plan, reasons to guit, and medications prescribed) in the weeks leading to the guit attempt (Week 5). At Week 0, participants will also receive an iCO Smokerlyzer mobile device for their personal use and will download the compatible Covita iCO app to their personal smartphones that displays CO readings. They will receive training on use of the iCO monitor and app and will be encouraged to measure CO levels as much as desired throughout the study period. Information will be stored on the apps on individuals' personal devices (no personal identifiers will be used and data will not be sent to or from participants, with anonymized data from the apps remaining on participants' phones).

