Acceptability questionnaire: Participants will complete a questionnaire developed by our team to rate the protocol from 1-10 in the following areas: perceived helpfulness, understandability, and likelihood of use at Weeks 8, 12, and 24 follow-ups in the intervention condition only. Total mobile app data usage of iCO and SQC will be recorded and participants will be asked to record usage of iCO or SQC apps daily on the TLFB paper log.

Focus Groups and Qualitative Interview: We will conduct semi-structured, audio-recorded telephone interviews (1) during the Focus Group Phase; and (2) at Week 8 of the Pilot RCT (with intervention condition participants only) to collect in-depth feedback about user satisfaction with features of the overall intervention and its components (telephone sessions, SQC app, iCO monitor). We will use a framework of open-ended questions based on interview guides developed by the study team. The semi-structured interview guides (attached) were developed using standard methodological approaches in qualitative research. We will inquire about individual components of the manual and perceived helpfulness; feasibility and acceptability of use in a real-world context; cost-effectiveness and scalability; acceptability in a military and veteran cultural context; role of stigma; and anticipated barriers and facilitators of implementation in both rural and urban settings. We will also discuss the strengths and weaknesses of traditional telephone-delivered sessions as compared with newer smartphone technologies for session delivery (i.e., mobile video

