6.4.5 Handling of Missing Data

Missing data can arise from several sources, including participant dropout or participant failure to complete occasional measures. For the analyses of smoking outcomes, we will conduct analyses in two ways: a complete-case approach using observed data, and to assume missing as the negative outcome (e.g., missing=non-abstinent) to obtain a range of the intervention effects. We will use the maximum likelihood approach of the mixed model to accommodate missing outcome variables without bias under the assumption of missing at random, meaning that missingness is random conditional on observed variables. This is a reasonable assumption for missing data not under the participants' control and sporadic missing items on measures.

7 - Trial Administration

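### Relating cumulative app use to outcomes builds in a positive association for abstinence scored missing = non-abstinent, and for retention where logging ends with sessions

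*Combined protocol and SAP*

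**What the plan says.** Section 6.4.1 measures app use as "number of days each app is used per participant self-report and total data used by each app over the study period". It then plans to look at usage patterns "in intervention condition participants and examine the relationship between app usage and study outcomes". It names no model, exposure window, denominator or list of outcomes. In the same paragraph, NRT adherence does have a denominator (days prescribed).

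On how use is recorded, section 6.2 says "participants will be asked to record usage of iCO or SQC apps daily on the TLFB paper log". Section 6.1.3 describes the paper log as one "which will be mailed to the study team at each assessment time point". Section 6.1.4 says app data are not transmitted, "with anonymized data from the apps remaining on" participants' phones.

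On outcomes, sections 6.1.3 and 6.2.1 both state: "Participants with missing salivary cotinine or those unable to obtain verification from a friend or family member will be considered non-abstinent". Section 6.4.5 plans two analyses of smoking outcomes, one on observed data and one scoring missing as failure, and relies on mixed-model maximum likelihood for missing outcome values. Retention is four or more sessions (sections 4.1 and 6.4.1) or total sessions completed (section 6.3.1).

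**The concern.** A cumulative count can grow only while someone is still being recorded. A participant who leaves early has few recorded days of use and, under the missing-cotinine rule, is also non-abstinent. Leaving the study therefore lowers the exposure and fixes the outcome at failure. Retention raises the same problem more directly: if logging ends when sessions end, days of use and sessions attended both measure time in treatment. Most session outlines in section 6.1.1 also prompt app use.

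Time order is a separate matter. A total running to Week 24 includes use after the Week 8 and Week 12 outcomes.

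At stake is how a dose-response pattern would be read. Section 6.4.2 says the pilot exists to refine the intervention for a future trial, and this is the only planned quantitative link between use of the technology and outcomes.

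**Working it through.** The plan gives no figure for this analysis, so there is none to reproduce. The check asks what the planned total would show if the apps were inert.

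**Inputs from the documents**
- Intervention arm: 40 (section 5.1).
- Follow-up: 24 weeks = 168 days. Logs return at Weeks 8, 12 and 24 = days 56, 84 and 168.
- Dropout: no rate is stated. Section 6.4.2 works with at least 60 completers of 80, and 1 − 60/80 = 25%. A rate of 40% is used as a less favourable case.

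**Assumptions (not in the documents)**
- Daily use probability varies between people as Beta(1.5, 1.5), mean 0.5, independent of outcome.
- 25% of those followed to the end are abstinent.
- Dropout day is uniform over 168 days.
- The test is a two-sided 5% Mann–Whitney test.

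**Step 1. Expected recorded days of use**
- Completer: 168 × 0.5 = 84.
- Dropout, use known to the day of leaving: 84 × 0.5 = 42.
- Dropout, use known only from returned logs: 1/3 leave before day 56 (0 days logged), 1/6 between days 56 and 84 (56 logged), 1/2 later (84 logged). Mean logged days = 56/6 + 84/2 = 51.3, and 51.3 × 0.5 = 25.7.

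**Step 2. Gap between abstinent and non-abstinent, missing = non-abstinent**

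All abstinent participants are completers (mean 84). With dropout d and dropout mean m, the non-abstinent mean is [0.75(1 − d) × 84 + d × m] / [0.75(1 − d) + d].
- d = 25%, m = 42: (47.25 + 10.5)/0.8125 = 71.1; gap 12.9 days.
- d = 25%, m = 25.7: (47.25 + 6.42)/0.8125 = 66.1; gap 17.9 days.
- d = 40%, m = 42: (37.8 + 16.8)/0.85 = 64.2; gap 19.8 days.
- d = 40%, m = 25.7: (37.8 + 10.27)/0.85 = 56.5; gap 27.5 days.

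**Step 3. Simulated rejection rate with inert apps (nominal 5%)**

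| Dropout | Use known to day of leaving | Use known from returned logs only |
|---|---|---|
| 25% | about 9% | about 13% |
| 40% | about 15% | about 24% |

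The size depends on the assumed abstinence. In a separate run with Beta(2, 2) use, 25% dropout and abstinence of 15%, 30% and 50% among completers, rejection was 6.4%, 11.8% and 21.4% with use known to the day of leaving, and 7.8%, 17.8% and 38.0% with returned logs only.

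**Step 4. Where the artefact disappears or shrinks**
- Complete case: about 4–5%.
- Use counted over 8 weeks only, known to the day of leaving: a completer has 28 days. A dropout has (28/3 + 56 × 2/3) × 0.5 = 23.3. The gap is 28 − (0.5625 × 28 + 0.25 × 23.3)/0.8125 = 1.4 days at 25% dropout, and 28 − (0.45 × 28 + 0.40 × 23.3)/0.85 = 2.2 days at 40%. Simulated rejection was 4.5% and 5.0%.

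**Step 5. Retention over 8 weeks, 40% stopping early**

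The test rejects in 99% of null trials if logging ends with sessions, 42% if half of those who stop keep logging, and 15% if three quarters do. If all keep logging, a separate run gave 3.5–4.5%.

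**Step 6. Alternatives**

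Use per observed day rejected in 3.6–5.2% of null trials. Weeks 1–8 use among those still reporting at Week 8, related to later abstinence, rejected in 3.6–5.9%. Both are close to nominal.

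**The case against.** The strongest reply is that the plan already contains much of the remedy. Section 6.4.5 includes a complete-case analysis of smoking outcomes, where the artefact is absent under this null. The FTND and PCL-5 carry no failure score. Section 6.1.3 uses the phrase study period for eight weeks, and over eight weeks the abstinence artefact nearly vanishes. The same section invites people who stop treatment to complete follow-up, so their logs may continue and the 99% retention figure is a worst case. No document says that app use will be related to sessions attended, and no test or alpha is set for this analysis. At 25% dropout, 87–91% of null trials would still show nothing significant.

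All of this limits the point, but it does not remove it. Section 6.4.1 does not say which missing-data rule governs the app analysis, and the endpoint definition itself scores missing cotinine as non-abstinent. Sections 6.3.5 and 7.1 describe a 24-week study period, and logs are collected to Week 24, so the longer window is at least as natural a reading. Section 6.3.1 lists retention first among the primary outcomes, so it falls within unspecified study outcomes. Complete-case analysis does not help retention.

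A reader might also infer that use after the outcome inflates the association. The documents do not support a direction: people who quit could use a CO monitor more or less afterwards.

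**Conclusion.** The point holds in limited form and is minor. For abstinence scored missing = non-abstinent, with use totalled over 24 weeks, the planned measure shows quitters with about 13 to 27 more recorded days when the apps do nothing, and a 5% test rejects in about 9–13% of trials at 25% dropout and 15–24% at 40%. For retention the distortion runs from negligible to near certain, depending on how many people keep logging after they stop sessions. These sizes rest on assumed dropout, abstinence and use rates.

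Two stronger readings are not supported. One is that dropouts are scored as failures on every outcome, so that the association must appear; section 6.4.5 and the results above contradict that. The other is that this analysis would decide whether the app and monitor go forward. Section 6.4.1 ties revision of the protocol to the feasibility and acceptability objectives, including the SUS and session ratings, and not to this association.

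**What to change.** In section 6.4.1, define app use as days used divided by days logged, counted only up to the outcome being analysed (for example, the Weeks 1–8 log for Week 12 and Week 24 outcomes), among intervention participants who returned that log. Relate it to later outcomes using observed outcomes only, adjusted for the Week 0 value where one exists. State who counts as observed for abstinence, because sections 6.1.3 and 6.2.1 class missing cotinine as non-abstinent. Do not relate app use to sessions attended. Report the result as descriptive.

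A window ending before Week 8 is less practical: logs first arrive at Week 8, so earlier use is unknown for anyone lost before then, and use in quit week (Week 5) could be discarded.

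The change is to wording only and uses the same logs. The cost is that participants with no returned log are excluded, and later use is described but not tested.

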5.2.2 Secondary and Exploratory Outcome Variables (if applicable)

We will examine the effect of the technology- and telephone-intervention on daily cigarette, e-cigarette, and smokeless tobacco use; nicotine dependence (Fagerström Test of Nicotine Dependence16 [FTND]) and PTSD symptom levels (PTSD Checklist-517 [PCL-5]) at Weeks

8, 12, and 24; and bioverified seven- and 30-day point prevalence abstinence at Weeks 12 and 24.

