6.2 Assessments

Psychiatric history: VA electronic psychiatric record review (including current psychiatric diagnoses, current treatment, and any documentation of psychiatric acuity in past 30 days) will be reviewed by the PI at Week 0.

Clinician-Administered PTSD Scale (CAPS): The CAPS is a 30-item, structured interview that is the gold standard for DSM-V PTSD diagnosis and will be administered at Week 0 to assess for lifetime PTSD.

M.I.N.I. Neuropsychiatric Inventory: The M.I.N.I. 6.0 is a structured interview for DSM-V diagnosis of psychiatric disorders and will be administered at Week 0.

Timeline Follow-Back (TLFB): Use of cigarettes, e-cigarettes, chewing tobacco, and tobacco products using TLFB (past 30 days), which uses a calendar with specific anchor dates to identify the quantity and frequency of use. TLFB will be given at Weeks 0, 8, 12, and 24.

Medical history: VA electronic medical record review; medical history, medications and over the counter supplements; drug allergies will be completed by the PI at Week 0.

Demographic questionnaire: Age, education, relationship status, military branch and occupational specialty, deployment history, and living arrangements will be obtained at Week 0.

Tobacco use history: Age at initiation of cigarettes, e-cigarettes, and smokeless tobacco; history of quit attempts; longest time abstinent from cigarettes; current exposure to cigarettes in household will be obtained at Week 0.

Contemplation Ladder:⁷⁸ We will administer this brief measure of motivation to quit at Weeks 0, 8, 12, and 24.

Fagerström Nicotine Dependence Questionnaire (FTND): ¹⁶The FTND is a validated instrument to evaluate the intensity of physical addiction to nicotine. It will be administered at Weeks 0, 8, 12, and 24.

PTSD Checklist-5 (PCL-5): The PCL-5 is a 20-item self-report measure that assesses the 20 *DSM-V* symptoms of PTSD. The PCL-5 will be administered at baseline and at Weeks 0, 8, 12, and 24.

System Usability Scale (SUS): The SUS is a brief, reliable and valid instrument to measure perceptions of usability of technology devices, with higher scores reflecting greater usability (maximum score of 100). We will administer the SUS for the SQC app and iCO monitor at Weeks 8, 12 and 24 follow-ups in the intervention condition only.

Urine Pregnancy: At baseline and Week 4, female participants will complete a urine pregnancy test.

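### Section 6.4.1 gives the Week 0 value no stated role in the exploratory FTND, PCL-5 and daily tobacco-use comparisons, so precision available from data already collected is not secured

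*Combined protocol and SAP*

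**What the plan says.** Section 6.4.1 relies on randomization to balance covariates and then adds one exception: "If, however, the preliminary analyses indicate the treatment conditions vary on potentially confounding variables such as age or number of previous quit attempts", in which case "these covariates will be included in a multivariate model". It names no test, no cut-off and no closed list of variables.

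On the model, the same section says that "the most parsimonious model will be a general linear model for each outcome", without listing its terms. The comparisons it names include "FTND scores, and PCL scores (Exploratory Hypotheses) at Weeks 8, 12, and 24"; Week 0 is not mentioned. Section 6.4.5 adds "We will use the maximum likelihood approach of the mixed model to accommodate missing outcome variables", again without a role for baseline. Section 6.4.3.4 compares participant characteristics across categories of VA facility, not across arms.

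The Week 0 values will exist. For dependence, section 6.1.3 says "We will administer the FTND at Weeks 0, 8, 12, and 24", and it gives the PCL-5 the same schedule. For tobacco use, section 6.2 says "TLFB will be given at Weeks 0, 8, 12, and 24". Daily use is an exploratory outcome under section 5.2.2 ("We will examine the effect of the technology- and telephone-intervention on daily cigarette, e-cigarette, and smokeless tobacco use"), but it is missing from the comparisons listed in 6.4.1.

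**The concern.** For a score measured both before and after treatment, its own baseline is the obvious covariate to fix in advance. The plan instead ties covariate adjustment to whether the arms happen to differ, and its examples are age and previous quit attempts, not the baseline score. A baseline that predicts follow-up is worth including whether or not the arms look balanced, because it removes residual variance. A rule that waits for imbalance will usually leave it out.

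The stake is modest. Section 6.2.1 says that efficacy is not a primary aim, and these outcomes are exploratory. Section 6.4.2, however, gives effect-size estimation for a future RCT as one purpose of the pilot, and the width of the interval bears on that purpose.

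**Working it through.** **Inputs from the documents.** 80 randomized 1:1 (6.1.2, 6.4.2); at least 60 completers (6.4.2), so n = 30 per arm.

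**Assumptions, because the documents give no figure.** Two-sided 5%, 80% power, one follow-up, a roughly normal outcome with the same SD at Week 0 and follow-up, and a baseline-to-follow-up correlation r shown over a range.

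**The plan's own statement first.** Section 6.4.2 says that 60 completers give adequate power for large effects. Taking large as 0.8 SD (an assumption), the two-sample t-test with 30 per arm has 86% power. The statement is plausible, and nothing below contradicts it.

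**Detectable difference.**

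1. Week 0 ignored: standard error √(2/30) SD, 58 df, noncentral t. Result 0.736 SD.
2. Week 0 as covariate: the variance is multiplied by (1 − r²), and by a further (1 + 1/56) on average for chance Week 0 imbalance; 57 df. To three decimals the result is 0.736 × √[(1 − r²)(57/56)]. At r = 0.5 this is 0.736 × √(0.75 × 1.018) = 0.643.
3. Change from Week 0: the variance is multiplied by 2(1 − r). At r = 0.3 this is 0.736 × √1.4 = 0.87.

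| r | Week 0 ignored | Week 0 covariate | Change score | Mean 95% interval width with covariate (1.03 if ignored) |
|---|---|---|---|---|
| 0.1 | 0.74 | 0.74 | – | 1.03 |
| 0.2 | 0.74 | 0.73 | – | 1.02 |
| 0.3 | 0.74 | 0.71 | 0.87 | 0.99 |
| 0.5 | 0.74 | 0.64 | 0.74 | 0.90 |
| 0.7 | 0.74 | 0.53 | 0.57 | 0.74 |

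All entries are in SD units. Interval widths are means over 100,000 simulated trials per setting.

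**Where the gain stops.** Setting (1 − r²)(57/56) = 1 gives r = √(1/57) = 0.13. Below that the covariate costs slightly more than it returns. At r = 0 the mean width is 1.038 against 1.029, which is 0.9% wider. The gain is also an average: the adjusted interval is the wider one in 43%, 18% and 0.8% of simulated datasets at r = 0.2, 0.3 and 0.5.

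**What an imbalance trigger recovers.** Suppose the check were a p<0.05 test on the Week 0 score. Under randomization it fires in about 5% of trials, so Week 0 stays out of the model in the other 95%. Simulated results at a true difference of 0.6 SD:

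| r | Power, Week 0 ignored | Power, p<0.05 trigger | Power, always adjusted | Type I error, p<0.05 trigger |
|---|---|---|---|---|
| 0.3 | 63% | 63% | 66% | 4.7% |
| 0.5 | 63% | 63% | 74% | 4.3% |
| 0.7 | 63% | 64% | 89% | 3.6% |

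Such a rule recovers almost none of the gain and is slightly conservative.

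**The case against.** The strongest reply is that the plan is silent rather than wrong. The general linear model can hold the Week 0 value, the mixed model in 6.4.5 can too, and the open list of confounders could include it. Nothing says that Week 0 will be discarded, so the 0.74 SD comparator is the least favourable reading. That is correct. A reader might infer that the plan ignores baseline, and the text does not support that. What stands is that it does not commit to using it. If Week 0 were used through a simple change score, the covariate would still do better at each r shown, although by little at r = 0.7 (0.57 against 0.53 SD).

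A reader might also infer an inflated false-positive rate. If the analyst could report whichever of the adjusted and unadjusted results was significant, simulation gives 6.4% to 8.1% for r between 0.3 and 0.7. But 6.4.1 says that triggered covariates go into the model; it does not offer a choice between results, so those figures describe a freedom that the plan does not state.

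Further limits stand. The correlation is unknown. With 40 per arm the normal-approximation figures are smaller throughout: 0.63 SD unadjusted, then 0.60, 0.54 and 0.45 SD at r = 0.3, 0.5 and 0.7, without the allowance for chance imbalance. Section 6.4.2 does not tie its effect-size purpose to these three outcomes. Even at r = 0.5, an interval 0.90 SD wide remains imprecise.

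**Conclusion.** The point holds as an optional improvement to exploratory analyses. Covariates enter these three comparisons only through an undefined imbalance check, and Week 0 has no stated role. Against a comparison that ignores Week 0, committing to it as covariate narrows the mean interval by about 4%, 13% and 28% at r = 0.3, 0.5 and 0.7 (0.990, 0.900 and 0.742 against 1.029), with no gain at about r = 0.1. This rests on 30 completers per arm, one follow-up, near-normality and an assumed r. For daily tobacco use, where normality is least secure, the sizes are indicative only.

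It would go too far to read this as bias or as a fault in the main results. Under randomization the unadjusted comparison is unbiased, retention has no Week 0 value, and no Aim 1 or Aim 2 conclusion or stated figure changes. Nor does it follow that the sponsor's imbalance rule must go: removing adjustment for age or previous quit attempts is not needed for the gain.

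**What to change.** Add to section 6.4.1:

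> Each FTND and PCL-5 comparison, and each daily tobacco-use comparison, includes the Week 0 value of the same measure as a pre-specified covariate (or, in a mixed model, a Week 0 mean constrained equal across conditions), regardless of observed imbalance.

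Keep the existing imbalance sentence for other variables. The new sentence also names daily tobacco use, which the section's list of comparisons currently omits.

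The cost is wording and one degree of freedom per model, with no new data, visits or participants. If r is near zero, the mean interval widens by at most about 1%.
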